### 3.2 Exclusion Criteria

- Participants with a Pacemaker
- Participants with irregular heart rate or a heart rate lower than 60 beats per minute (bradycardia)
- Have had a transplant within the last 2 years
- Have had a heart attack or cardiac bypass surgery within the last 12 months
- History of substance abuse, including prescription drugs, within the last 12 months
- Patients with complaints of dizziness or lightheadedness within the last 3 months
- Women who are pregnant

- Participants with Diabetic Retinopathy
- Current Ear infection
- SBP < 100 and/or DBP < 60
- History of uncontrolled bipolar disorder within the last 12 months
- History of uncontrolled seizures within the last 12 months
- History of Aneurysms
- History of syncope within the last 12 months
- Participants that have had a TIA or stroke within the last 12 months
- Participants with health problems deemed at risk for the study by the Principal Investigator
- Participants with any changes to Pain/Anxiety/Depression/Sleeplessness medications within last 60 days (participants that do not meet this medication-change washout period may be delayed until 60-day period is met)
- Participants that are currently under adjudication process for disability support, VA or other

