## 4.0 STUDY PROTOCOL

The Nu-V3 Clinical Study is a prospective, single-arm, open-label, multi-center study using the Nu-V3 cranial nerve stimulation treatment device in patients with pain, anxiety, depression, and/or sleeplessness.

For this Phase I study, a total of 50-100 patients at multiple centers will be registered for study participation. Study participants are those who have signed the informed consent form, met the inclusion and exclusion criteria, and are enrolled in the study at one of multiple sites. Enrolled participants are stratified based on their pain, anxiety, depression, and/or sleeplessness symptom presentation at baseline and treated with the Nu-V3 device for 8 weeks, then observed for an additional 4 weeks. Interim analysis of reported data will be based on baseline stratifications and conducted at 4, 8, and 12 weeks during this time. Post study, participants will be given the chance to continue with an optional maintenance treatment with the Nu-V3 device per a 2-weeks on, 2-weeks off schedule, for an additional 12 weeks, with an 8-week observation.

Subjects enrolled onto the Nu-V3 Clinical Trial will undergo the following regimen:

- At the baseline visit, patients will be asked to complete study questionnaires (Appendix 11) regarding all of the following symptoms: pain, anxiety, depression, and/or sleeplessness, as well as their quality of life, active medications, medical history, and demographical information.
- At each subsequent visit, patients will be asked to complete study questionnaires regarding all the following symptoms: pain, anxiety, depression, and/or sleeplessness, as well as their activity level and quality of life.
- The sessions will begin with the Nu-V3 device being placed on the left ear and three small pads (non-invasive) being placed on the ear. Each Nu-V3 device

lasts for up to 14 days with a change in the pads approximately 7 days into the treatment.

- Each session takes approximately 15-20 minutes. The placement of the device takes approximately 5 minutes and the remaining time is spent verifying ePRO form completion, and evaluating the patient for all device effects.
- The Nu-V3 device is mobile and is worn externally on the left ear 24 hours a day during treatment, fitting comfortably behind the ear. An electrical signal is sent to the external ear through coated wire leads attached to the device and adhesive pads which attach to three sites on the ear.

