- Participants should be able to perform their typical day-to-day activities while wearing the device. They may shower while wearing the Nu-V3 device, provided that they do not get the device wet and use the small disposable ear covers that are provided for them.
- Patients should not change their existing forms of treatment or medications without discussion with the investigator.
- Nu-Life reserves the right to capture video, photographs and written testimonials from patients with written permission. In the event subjects elect to participate in any or all of these activities, they will be asked to sign a waiver giving exclusive rights to Nu-Life for the materials gathered from the patient, such as video, photographs and written testimonials. Their participation in this study is not dependent upon their willingness to provide these testimonial materials.

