## 5.0 DATA COLLECTION AND RETENTION

The study endpoints data will be collected from each participant's study questionnaires. The data will be collected electronically via the patient's own device, and uploaded to an electronic data capture system. Only patient data from the stratified indication(s) will be used for analysis of symptom response. The data will be used to demonstrate that the Nu-V3 device provides participants with relief of the symptoms of pain, depression, anxiety and/or sleeplessness. The data analysis will include comparative data for each participant's questionnaire prior to beginning treatment with the Nu-V3 device, the participant's weekly questionnaires during

treatment and the questionnaire completed at the end of the treatment with the Nu-V3 device.

Interim analyses of available data will be regularly submitted to the FDA for review.

The Principal Investigator at each site will be responsible for recording, collecting, and storing the research participant's study data. The written records must be stored in a secure location. Only the Principal Investigator or designated study staff will have access to the study records and all electronic files will be password protected. The Principal Investigator will also maintain adequate records for the study including:

- all correspondence with the IRB and Sponsor
- other pertinent data related to the study

All records are to be retained by the Principal Investigator for a period of seven (7) years following the closure of the study. Following study closure, the Principal Investigator shall inform Nu-Life of the location of study records and storage changes (i.e. the Principal Investigator leaves the institution where the study was conducted). In such cases, the study records may be transferred to another institution, investigator, or to Nu-Life upon written agreement between the Principal Investigator and Nu-Life.

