## 8.0 STUDY ENDPOINT and DATA ANALYSIS

### 8.1 Primary Endpoints: Primary endpoints consisted of the following:

Safety: The primary safety endpoint is the occurrence of reported unanticipated problems involving risk to subjects or others (“UPIRTSOs”). These UPIRTSOs are defined as those problems which alter the risks to subjects or others. This includes any study suspensions or holds. The primary safety endpoint analyses will be based on a risk-benefit conclusion.

Effectiveness: The primary effectiveness endpoints are an overall change in median reported symptoms of pain, anxiety, depression, and/or sleeplessness via numeric rating scales at 8 weeks. This primary effectiveness is measured by median reported symptom changes in pain, anxiety, depression, and/or sleeplessness for respective stratified populations via the following validated tools: Pain - Pain Intensity and Interference (PEG\_Scale), Anxiety - Generalized Anxiety Disorder 7-item (GAD-7) scale, Depression - Patient Health Questionnaire (PHQ-9), Sleeplessness - PROMIS short form 4a, and overall improvement of quality of life (QOL) - Patient’s Global Impression of Change (PGIC).

The hypothesis-driven criterion of effectiveness is to show that there is a statistically significant reduction in the median reported pain, anxiety, depression, and/or sleeplessness levels of patients using the Nu-V3 device. The second criterion is intended to show that there is a statistically significant improvement in reported quality of life and perceived treatment benefit, secondary to overall reported symptom reductions of pain, anxiety, depression, and/or sleeplessness.

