### 8.3 Sub-Analyses: Sub-Analyses Consist of the following:

The sub-analyses endpoints consist of the mean number of weeks that pain, anxiety, depression, and sleeplessness response are achieved and sustained, without utilization of another device, during the 8-week intervention. In addition, study sub-analyses also include the mean number of weeks to initial benefit from Nu-V3 device use, and the mean medication dosage reduction of short acting pain, anxiolytics, and/or insomnia. The device's comfort-of-use, and patient's perceived treatment benefit will also be captured for sub-analyses.

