	
 • Value of any parameter derived from the outcome measure data (e.g., hazard ratio, mean difference, correlation coefficient) 
 ○ Any of the following, if available: 
 ▪ Confidence Interval ▪ Standard deviation or standard error ○ Additional explanatory comments to interpret the value, if needed: 
 ▪ Directionality of comparison. For subtraction (i.e., A – B or B – A) or a ratio (i.e., A/B or B/A) 	[*]Estimation Parameter and Value Confidence Interval Parameter Dispersion Estimation Comments

*Required
 [*] Conditionally required

Figure 3.25- Statistical Analysis Checklist- Quality of Life Level

Insert Summary of Results Here

Reduction of Total Daily Dosage: Indication- Relevant Medications Taken (Baseline, 30, 60, 90 Days)

Outcome Measure Data Preparation Checklist

Overview: A tabular summary of outcome measure results by comparison group. You must report tables for each pre-specified primary and secondary outcome and any appropriate statistical analyses. The outcomes that were pre-specified in the Protocol Section of the record will be available to use and edit during results data entry. You may also include other pre-specified and *post hoc* outcomes. Use this checklist with the [Outcome Measure Simple Results Template](#)^Δ and [Results Data Element Definitions](#).

	Information to have available for each Outcome Measure	Term
	
 Label the measure as Primary, Secondary, Other Pre-specified, or Post hoc. 	* ^Δ Outcome Measure Type

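### Symptom drugs may change during the 8 treatment weeks, but the uncontrolled Week-8 analysis does not separate drug effects from device effect, and medication analyses are framed only as reductions

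*Protocol*

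**What the plan says.** Before entry, Protocol 3.2 excludes "Participants with any changes to Pain/Anxiety/Depression/Sleeplessness medications within last 60 days", with the option of waiting until the 60 days have passed. After entry, the rule in Protocol 4.0 is "Patients should not change their existing forms of treatment or medications without discussion with the investigator", and the SAP's design summary repeats it. It sets no limit on direction, drug, size or timing.

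The study is a "prospective, single-arm, open-label, multi-center study". Protocol 8.1 seeks a "statistically significant reduction in the median reported pain, anxiety, depression, and/or sleeplessness levels of patients using the Nu-V3 device", with 8 weeks as the primary time point, and the SAP's Primary Endpoints text agrees. The comparison is within patient; Protocol 5.0 states that "The data analysis will include comparative data for each participant's questionnaire prior to beginning treatment with the Nu-V3 device", set against the weekly and end-of-treatment questionnaires.

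Two medication analyses are planned. Protocol 8.3 lists "the mean medication dosage reduction of short acting pain, anxiolytics, and/or insomnia", and the SAP repeats it. SAP Section 3.0 has an outcome headed "Reduction of Total Daily Dosage: Indication- Relevant Medications Taken (Baseline, 30, 60, 90 Days", with templates titled as a dosage decrease. The schedule in Protocol 4.1 has a Medications Form at Weeks 1, 4, 8 and 12.

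**The concern.** The entry rule requires stable symptom medication for 60 days. The documents do not say why, but a stable baseline is the evident purpose. That protection ends at enrolment, although what happens between baseline and Week 8 matters just as much to a before-after comparison. With no control group, nothing absorbs the effect of a drug started or increased during treatment, and improvement that the drug caused enters the same score change that is read as device effect.

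The medication analyses do not close the gap. They are framed around reductions, so a report that followed the plan could show a dosage reduction and a symptom improvement without saying how many improved patients had started or increased a drug for that symptom. The Protocol's list of drug classes also leaves out antidepressants, although depression is one of the four primary symptoms. The SAP calls the study the primary pivotal one for its De Novo request, so a regulator is likely to ask how many patients changed symptom drugs.

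**Working it through.** **Textual check.** I looked in both documents for any rule on medication change in the effectiveness analysis.

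- Exclusion, censoring, adjustment, non-response scoring or a sensitivity analysis for changed symptom drugs: none.
- Imputation: SAP Section 5.0 describes it for the safety endpoint only.
- Co-interventions: the one condition in an effectiveness analysis is use of another device, in the duration-of-response sub-analysis of Protocol 8.3. Drugs are not mentioned.
- Early exit: medication change is not among the reasons listed under Accountability in the SAP, although that list is open-ended.
- Primary test: none is named. SAP Section 5.0 has a placeholder.

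**Size.** The plan states no alpha, SD, effect or power, so there is no figure of its own to reproduce. What follows is illustration only.

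Inputs from the documents: "a total of 50-100 patients at multiple centers will be registered for study participation". This is the whole Phase I enrolment; a symptom stratum may be smaller, so n=25 is included.

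Assumed inputs, not in the documents: true device effect and natural change zero; baseline-to-Week-8 correlation 0.6; a share f of the stratum raises a symptom drug and gains d SD of the score; nobody reduces; two-sided 5% test, so 2.5% in the favourable direction.

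For a test of the mean change:

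- shift = f × d
- SD of change = √[2(1 − 0.6) + f(1 − f)d²]
- favourable rejection = Φ(shift × √n / SD − 1.96)

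With f = 20% and d = 1: shift = 0.20; SD = √(0.80 + 0.16) = 0.980.

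- n=25: Φ(1.02 − 1.96) = 17%
- n=50: Φ(1.44 − 1.96) = 30%
- n=100: Φ(2.04 − 1.96) = 53%

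With f = 30% and d = 1: shift = 0.30; SD = √(0.80 + 0.21) = 1.005.

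- n=50: Φ(2.11 − 1.96) = 56%
- n=100: Φ(2.99 − 1.96) = 85%

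With f = 10% and d = 0.5: shift = 0.05; SD = √(0.80 + 0.0225) = 0.907.

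- n=50: Φ(0.39 − 1.96) = 6%
- n=100: Φ(0.55 − 1.96) = 8%

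**Rank-based and sign tests.** The endpoint is worded as a median, so the mean test may overstate the effect. For an exact sign test at f = 20%, d = 1, the chance that a patient improves is 0.80 × 0.5 + 0.20 × Φ(1/√0.80) = 0.574. The test rejects at 33 or more improvers of 50 (14%) or 61 or more of 100 (26%). A simulated Wilcoxon signed-rank test under the same assumptions falls between the two: 25% at n=50 and 48% at n=100. If d is instead measured in SDs of the change score, the simulated Wilcoxon figure at n=50 is 22%.

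**Reductions.** Keep f = 20%, d = 1, n=50 and the mean test, and let 10% of patients reduce a drug and lose 1 SD. The shift is 0.20 − 0.10 = 0.10, the SD is √(0.80 + 0.30 − 0.01) = 1.044, and the rate is Φ(0.68 − 1.96) = 10%. If 20% reduce, the shift is zero and the rate returns to 2.5%.

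**The case against.** The strongest reply is that drug changes may cut either way. The rule in Protocol 4.0 is neutral, and both documents expect reductions, which would tend to worsen the Week-8 score and count against the device. This stands. A reader might infer a bias that always favours the device; the documents do not support that, and the arithmetic shows reductions can offset it.

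A reader might also infer that only short-acting drugs are analysed. The SAP's total-daily-dosage outcome covers indication-relevant medication generally, and it could be computed net of increases. Neither document says so, and a net dosage figure would still leave the symptom result uncorrected.

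It is fair to add that no sentence permits increases by name or credits them to the device. Both follow from a rule that does not bar them, an uncontrolled comparison and the absence of any handling step. The larger gap is that no primary test is specified at all, and handling of drug changes is one part of it. Analysing Week-8 scores regardless of medication is a recognised strategy if it is chosen openly and disclosed. This is why the remedy below is supportive and is not a condition for a symptom claim.

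The percentages rest on assumed shares and effects. Those at n=100 need every patient at maximum Phase I enrolment to belong to one symptom stratum.

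**Conclusion.** The concern holds in limited form. Symptom-drug changes are possible during treatment, the baseline-to-Week-8 comparison has no step that separates them from device effect, and the planned medication analyses are framed as reductions. Increases bias the result towards the device and reductions against it; the net sign cannot be known from the documents.

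If increases predominate, the effect could matter. With an inert device, correlation 0.6, 20% of a stratum gaining 1 SD and nobody reducing, the favourable false-positive rate is roughly 14-30% at n=50 (sign test to mean test) and about 17% at n=25 (mean test), against 2.5%. With 10% of patients and 0.5 SD it is small, about 6-8% at n=50-100. These figures show what the plan cannot rule out. They do not predict what the trial will find.

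**What to change.** Keep the primary Week-8 analysis and add to the SAP:

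1. A supportive analysis per stratum. A patient whose Medications Form shows a new or increased drug for that stratum's symptom before Week 8 gets no credit for improvement: the change is set to zero, or to the observed change if that is worse. The second clause matters, because setting every such patient to zero would flatter someone who increased a drug and still deteriorated.
2. A table per stratum of patients with increased, unchanged and decreased symptom medication, so that both directions are visible.
3. The dosage endpoint computed as net change, so that increases count.
4. Both symptom results reported together. If they disagree, the improvement is not attributed to the device alone.

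The cost is SAP text, programming and a somewhat more conservative supportive estimate; a patient who truly benefited from the device but also increased a drug loses credit in it. The supportive analysis does not correct for reductions, which the table would show. No new visits are needed, provided the Medications Form, whose content is not shown in the text available, records drug and dose with enough detail to place a change before Week 8. No change to clinical care is proposed.

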#### 4.1 Phase I Study Assessment Tables

Nu-Life Solutions Miniaturized Wearable Medical Technology - Nu-V3		Study Treatment Assessments Table										Nu-V3
		*Evaluations are completed weekly, every 7 days =3 days										
Evaluation*	Study Treatment											
	Week 1	Week 2	Week 3	Week 4	Week 5	Week 6	Week 7	Week 8	Week 9-11	Week 12		
Informed Consent	x											
Inclusion and Exclusion 	x											
Patient Registration 	x											
Medications Form 	x			x				x		x		
Patient Onboarding and Orientation 	x											
In office assessment	x	x	x	x	x	x	x	x		x		
New Device Placed	x		x		x		x					
Pad Replaced		x		x		x		x				
Treatment Forms 	x	x	x	x	x	x	x	x				
No Device									x	x		
ePRO Questionnaires 	x	x	x	x	x	x	x	x	x	x		
Patients' Global Impression of Change ePRO form (PGIC) 		x	x	x	x	x	x	x		x		
Providers' Global Impression of Change ePRO form (PGIC)		x	x	x	x	x	x	x		x		
Family Global Impression of Change ePRO form (PGIC)		x	x	x	x	x	x	x		x		
Optional Patient Media Testimony	x			x				x		x		

1. Inclusion/Exclusion, Registration, Medications, Treatment forms to be completed by site coordinator via online module.  
 2. Patient Onboarding and Orientation includes introductory demographics form, Nu-V3 patient training video  
 3. ePRO questionnaires completed on patient's mobile device: DQ-9 (baseline), PTB-7, PEG, GAD-7, PHQ-9, PROMIS 4a, PGIC  
 4. If patient consents to media testimony, site will collect via study collection process every 4 weeks.

Evaluation*	Post Study Intervention Assessments Table														
	*Evaluations are completed weekly, every 7 days ±3 days														
	Optional Maintenance Therapy										Long Term Follow Up				
Week 13	Week 14	Week 15-16	Week 17	Week 18	Week 19-20	Week 21	Week 22	Week 23	Week 24	Week 25	Week 26	Week 27-28	Week 29	Weeks 30-31	Week 32
Medications Form 				x			x			x					x
In office assessment	x	x		x	x		x	x							
New Device Placed	x			x			x								
Pad Replaced		x			x			x							
Treatment Forms 	x	x		x	x		x	x							
No Device			x			x			x	x	x	x	x	x	x
ePRO Questionnaires 	x	x		x	x		x	x	x	x		x			x
Patients' Global Impression of Change ePRO form (PGIC) 	x	x		x	x		x	x				X			X
Providers' Global Impression of Change ePRO form (PGIC)		x			x			x				X			X
Family Global Impression of Change ePRO form (PGIC)		x			x			x				X			X
Optional Patient Media Testimony		x			x			x				x			X

1. Inclusion/Exclusion, Registration, Medications, Treatment forms to be completed by site coordinator via online module.
2. Patient Onboarding and Orientation includes introductory demographics form, Nu-V3 patient training video
3. ePRO questionnaires completed on patient's mobile device: DQ-9 (baseline), PTB-7, PEG, GAD-7, PHQ-9, PROMIS 4a, PGIC
4. If patient consents to media testimony, site will collect via study collection process every 4 weeks.

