### 8.2 Secondary Endpoints: Secondary endpoints consisted of the following:

Effectiveness: The secondary effectiveness endpoint is an overall change in median reported symptoms of pain, anxiety, depression, and/or sleeplessness for respective stratified populations via numeric rating scales at 4, 8, and 12 weeks. This is measured via the following validated tools: Pain – Pain Intensity and Interference (PEG\_Scale), Anxiety - Generalized Anxiety Disorder 7-item (GAD-7) scale, Depression - Patient Health Questionnaire (PHQ-9), Sleeplessness - PROMIS short form 4a, and overall improvement of quality of life- Patient’s Global Impression of Change (PGIC).

The patient’s perceived treatment benefit and device comfort information will be captured via the non-validated tool, Perceived Treatment Benefit Form (PTB-7). This effectiveness tool will measure median levels of reported perceived treatment benefit and device comfort.

The hypothesis-driven criterion is to show that there is a statistically significant reduction in the median reported pain, anxiety, depression, and/or sleeplessness levels of patients using the Nu-V3 device at weeks 4, 8, and 12. The second criterion is intended to show that there is a statistically significant improvement in reported quality of life and perceived treatment benefit secondary to overall reported symptom reduction of pain, anxiety, depression, and/or sleeplessness at weeks 4, 8, and 12.

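### Sponsor-owned patient testimony is scheduled before the self-rated Week 8 primary and Week 12 secondary outcomes, in a study with no control arm to absorb its effect

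*Protocol*

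**What the plan says.** Protocol 4.0 provides that "Nu-Life reserves the right to capture video, photographs and written testimonials from patients with written permission". A patient who agrees signs a waiver giving the sponsor exclusive rights. Agreement is voluntary: "Their participation in this study is not dependent upon their willingness to provide these testimonial materials".

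The Protocol 4.1 assessment table has a row for "Optional Patient Media Testimony", marked at Weeks 1, 4, 8 and 12. Footnote 4 gives the task to the site: "If patient consents to media testimony, site will collect via study collection process every 4 weeks". The SAP's Study Treatment Assessments Table carries the same row and footnote.

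On outcomes, Protocol 8.1 states: "The primary effectiveness endpoints are an overall change in median reported symptoms of pain, anxiety, depression, and/or sleeplessness via numeric rating scales at 8 weeks". Protocol 8.2 sets the secondary endpoint "for respective stratified populations via numeric rating scales at 4, 8, and 12 weeks". The instruments come from the patient: "ePRO questionnaires completed on patient's mobile device: DQ-9 (baseline), PTB-7, PEG, GAD-7, PHQ-9, PROMIS 4a, PGIC". Protocol 4.0 describes a "prospective, single-arm, open-label, multi-center study".

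**The concern.** The testimony visits coincide with the baseline visit and with every primary and secondary outcome visit. By Week 8 a patient may already have told the treating site, in material the sponsor owns, what he or she thinks of the device. The same patient then rates symptoms and global change in a study where that site takes part in every visit. A person who has gone on record may wish to stay consistent. If the statement was favourable, that wish pushes the rating towards benefit.

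PGIC is the most exposed measure, because it asks how much the patient has changed since starting treatment at the clinic, which is close to what a testimonial invites.

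In a controlled trial both arms would share such an influence and much of it would cancel. Here the estimate is change from baseline in one unblinded group, so any shift enters it whole. No endpoint in Protocol 8.1 to 8.3 uses the testimony, so the analysis does not need it before the last outcome.

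**Working it through.** The plan gives no figure on this point to reproduce. The check is of timing, followed by an illustration of sensitivity.

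**Timing.** Testimony weeks come from the 4.1 table, outcome weeks from 8.1 and 8.2.

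| Rating | Role | Testimony at earlier visits | Testimony at the same visit |
|---|---|---|---|
| Week 4 | secondary | Week 1 | Week 4 |
| Week 8 | primary and secondary | Weeks 1 and 4 | Week 8 |
| Week 12 | secondary | Weeks 1, 4 and 8 | Week 12 |

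The earlier-visit column does not depend on the order of tasks within a day. The Week 4 testimony matters most for the primary endpoint: it comes during treatment, four weeks before the rating. Week 1 is the baseline and first-placement visit, so testimony there can voice expectation or severity but not experienced benefit.

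**Safeguards.** The readable text of the two documents does not put the questionnaires before testimony at a visit, does not defer testimony past the outcomes, and does not plan to record testimony status in the analysis.

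**Illustration 1, in SD units.** Assumptions, none from the documents: no true change; a share f of patients gives testimony; their change scores shift by d SD; one-sample two-sided normal test of the mean at 0.05. The plan names no test and no significance level.

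- Mean shift m = f × d; SD of the mixture s = √(1 + f(1 − f)d²).
- λ = m√n / s; rejection rate = Φ(λ − 1.96) + Φ(−λ − 1.96).
- Example with f = 0.25, d = 0.5, n = 50: m = 0.125; s = √(1 + 0.1875 × 0.25) = 1.023; λ = 0.125 × 7.071 / 1.023 = 0.864; rate = Φ(−1.096) + Φ(−2.824) = 13.9%.

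| f | d | n = 50 | n = 100 |
|---|---|---|---|
| 25% | 0.2 | 6.4% | 7.9% |
| 25% | 0.5 | 13.9% | 23.1% |
| 50% | 0.2 | 10.8% | 16.9% |
| 50% | 0.5 | 40.3% | 67.9% |

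The sizes 50 and 100 are the enrolment limits in Protocol 4.0. Protocol 5.0 analyses each symptom only in patients stratified to it, so a stratum may be smaller.

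**Illustration 2, on the 0–10 PEG.** Assumed: SD of change 2.5 and a 1-point shift among those giving testimony. Mean shift = share × 1 point. The chance of a significant reduction is 1 − Φ(1.96 − shift/SE), against a nominal 2.5% in that direction. SE = 2.5/√50 = 0.354, or 2.5/√25 = 0.50.

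| Share | Mean shift | n = 50 | n = 25 |
|---|---|---|---|
| 10% | 0.10 | 4.7% | 3.9% |
| 25% | 0.25 | 10.5% | 7.2% |
| 50% | 0.50 | 29.3% | 16.9% |

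Both illustrations test a mean, whereas the endpoint is a change in median. A shift in a minority of patients need not move a median by share × shift. The tables show direction and sensitivity; they are not estimates.

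**The case against.** The case against has real weight.

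- Testimony is optional, needs written permission and is not a condition of participation. It may be written or photographic as well as video, and nothing requires it to be favourable. A reader might infer that patients praise the device on camera before they score it; the documents do not say so. This limits who is exposed and how sure one can be of the effect, but it leaves the schedule as it is.
- A reader might infer that testimony comes before the questionnaires on the day. Task order may be in the visit process maps of Appendix 3, whose content is not available here. Only testimony from earlier visits is certain to precede a rating, and the point rests on that alone.
- A reader might infer that every effectiveness result is a self-rating. It is not: medication dose reduction is a sub-analysis (Protocol 8.3; item 2 under the SAP's secondary endpoints), and the site coordinator completes the Medications form. The point covers the primary and secondary symptom and PGIC measures.
- A reader might infer that the material is for promotion. The readable text gives the sponsor exclusive rights but states no use, and the media consent in Appendix 2 is not available here.
- Patients already give a view of benefit on PTB-7 and PGIC at each weekly visit from Week 2, before the Week 8 rating. Much of any consistency effect could arise without testimony, and the larger weakness is the uncontrolled, open-label design. This stands, and makes testimony a secondary contributor. Unlike those questionnaires, though, it feeds no endpoint and can be moved without loss of data.

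**Conclusion.** The concern holds as a matter of timing. Both documents schedule site-collected, sponsor-owned testimony at visits before the Week 8 primary ratings and the Week 12 secondary ratings. Because these are self-ratings in one unblinded arm, a shift caused by consistency with an earlier favourable statement would look exactly like a device effect.

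The stronger conclusion, that the results are biased by a known amount, is not supported. Uptake, content and effect of the testimony are all unknown, and the rejection rates above follow from an assumed share, shift and (for the PEG) SD, with a test of means. What can be said is that the schedule allows an avoidable influence that would favour the device if testimony is favourable, and that nothing in the readable plan guards against it.

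**What to change.** In the Protocol 4.1 study treatment table and its footnote 4, and in the SAP copy, delete the testimony marks at Weeks 1, 4 and 8. State that testimony may be taken only after the Week 12 ePRO questionnaires and PGIC have been submitted. The marks in the post-study table fall after Week 12 and can stay.

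If testimony has already been taken, record who gave it and when, and report Week 8 results by testimony status as description only. Dropping those patients would not correct the estimate: giving testimony is a choice made after baseline, and responders may be likelier to volunteer. A smaller change among the rest could reflect that selection and not biased scoring.

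The cost is an amendment to one row and one footnote in each document. The sponsor loses testimony footage from before Week 12. No outcome data are lost and clinical management is unchanged.
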